5 STUDY SCHEDULE

- Recruitment of interviewees will commence once ethical approval and local research governance permissions have been obtained.
- Interviewees will include patients and their carers, and staff (Section 7)
- Approaching potential interviewees:
 - Research nurses embedded within the clinical services will work with the clinical team to identify patient interviewees who meet the inclusion criteria. Once the clinical team confirm that a patient is willing to be approached, the research nurses will then discuss the research with the patient (Section 6). If patients are happy to be contacted by a researcher, the research nurse will either pass on the researcher's contact details to the patient or ask the patient if they are happy for their details to be passed onto the researcher.
 - Researchers will approach potential staff interviewees, guided by inclusion and exclusion criteria (Section 6).
- Recruitment: Researchers will contact potential interviewees and share study information. Potential interviewees will have at least 48 hours in which to consider whether they would like to take part.
- Consent: interviews will take place only with written, informed consent.
- Participation: interviews will last approximately 45 minutes and will be guided by a semistructured topic guide.
- Follow-up:
 - Patient and carer interviews will be single events; there will be no follow-up interviews.
 - Staff interviews may sometimes involve follow-up events, e.g. in the event that there is a significant change in services.
- Withdrawal: Interviewees will be free to withdraw at any time, up to two weeks after the interview has taken place. If they withdraw, all interview data provided will be removed from the dataset and destroyed securely.
- End of study will be reached when all data have been collected and analysed, and draft final report submitted to funder (deadline 14th September 2023).

6 ELIGIBILITY CRITERIA

6.1 Inclusion Criteria

For the qualitative work, interviews will be conducted with patients (and their carers, if appropriate) and members of staff with experience of prehospital video triage for suspected stroke.

The study will recruit patients who:

- are over 18 years of age
- any sex or gender
- have capacity to give informed consent
- underwent prehospital video triage for suspected stroke in participating services (NC London, East Kent, Darent Valley, Maidstone)
- were transferred to stroke unit or emergency department, referred to TIA clinic, or advised to stay home
- represent a range of backgrounds (including ethnicity, first language, socioeconomic status, home living arrangement)

The study will seek to recruit carers of recruited patient interviewees (e.g. family member or partner) to take part in a joint interview with the patient.

The study will seek to recruit staff with a range of roles related to prehospital video triage:

- Working in the participating areas (NC London, East Kent, Darent Valley, Maidstone)
- Ambulance staff (clinicians and managers)
- Stroke staff (clinicians and managers)
- Emergency department staff (clinicians and managers)
- Senior management (e.g. of hospital and ambulance organisations)
- Wider context (e.g. system leaders, commissioners, patient groups)

6.2 Exclusion Criteria

Participants will be excluded if they are under 18 years of age.

Patient participants will be excluded from the study if they have not undergone prehospital video triage for suspected stroke in the participating areas.

Staff participants will be excluded if they have not been involved in prehospital video triage for suspected stroke in the participating areas.

7 RECRUITMENT

Stakeholder interviews

A range of stakeholders will be interviewed (see Table 2), guided by the research questions. Adult patients and carers who have experienced the prehospital triage services will be interviewed, with the aim of understanding how people experienced different outcomes of assessment (transfer to stroke unit or emergency department, referral to TIA clinic, advised to stay home). It is important that the research examines how these new services are experienced by patients and carers whose first language is not English and will thus seek to recruit at least one such person in each case, conducting these interviews using UCL-approved interpreter services.

The team recognises that the issues covered in interviews of this kind may be stressful for patient, carer, and staff participants. Therefore, researchers will work closely with patient, voluntary sector, and clinical partners to ensure the interview process and topics minimise participant burden and risk of stress. The team will also ensure these activities are conducted only with full ethical and research governance approvals. The majority of participants (and all patient and carer participants) will take part in a single interview, lasting approximately 45 minutes, at a time and location of their choosing, with participation entirely voluntary and only with fully informed consent.

Patient and carer interviews: Research nurses embedded within the clinical services will work with the clinical team to identify and approach potential patient interviewees who reflect the research sample, covering a range of experiences of the prehospital video triage service (transfer to stroke unit or emergency department, referral to TIA clinic, advised to stay home) and a range of patient backgrounds (ethnicity, first language not English, socioeconomic status, home living arrangement). Once the clinical team confirm that a patient is willing to be approached, the research nurses will then discuss the research with the patient. They will share the Participant Information Sheet and discuss what the research will involve. The research nurses will also ask the patient if they have a carer (e.g. partner or family member) who might also wish to take part in the interview; if a carer is identified, the research nurse will also share study information with them. If patients (and carers, if appropriate) are happy to be contacted by a researcher, the research nurse will either pass on the researcher's contact details to the patient or ask the patient if they are happy for their details to be passed onto the researcher.

Therefore, the research team will only receive personal contact details of patients and carers who have agreed for this information to be passed on to them.

In line with good practice and UCL requirements, recruitment documentation (i.e., patient information sheets, carer information sheets and consent forms) will make clear the anticipated burden and risks of participating and emphasise the voluntary nature of participation. To ensure non-English speakers may take part in the patient and carer interviews, the interview Participant Information Sheets (Patient and Carer) will be translated into 12 commonly spoken languages by a professional translation company, and the team have budgeted for professional interpreters to facilitate a proportion of the interviews. There will be no payments to cover patient or carer participation: interviews will be conducted remotely (by telephone or online) or in the patient's or carer's home, meaning no reimbursement for travel will be required. Research nurses will maintain anonymised log will be kept of recruitment approaches and the research team will log interviews completed.

Staff interviews: Researchers will approach potential staff participants initially by sharing study information by e-mail or post. In line with good practice and UCL requirements, recruitment documentation (i.e., information and consent forms) will make clear the anticipated burden and risks of participating and emphasise the voluntary nature of participation.

Non-participant observations

The approach to recruitment, consent, and conduct of observations will be informed by the team's previous work in stroke and other clinical settings, and advice from our clinician and patient co-investigators.^[7, 29] Researchers will seek to ensure that staff are fully aware of the

research both before and during observations (e.g. through presentations to staff meetings), that staff have the opportunity to provide informed consent, and that they are assured that the researcher will withdraw from any situation where it is felt that observation is not appropriate or might interfere with provision of care.

Permission to observe *staff training sessions or meetings* will be obtained from activity leads (e.g. lead consultant, trainer, or meeting chair) in advance of the observed activities taking place. Participant information sheets will be circulated with meeting papers to all attendees. On first attendance (e.g. at meetings), the researcher will brief attendees on the study's aims, what participation entails, and that they may decline to participate at any time. At subsequent meetings, the researcher will announce him/herself as a non-participant observer, and confirm that he/she is happy to answer any questions in relation to the research.

Observations of ambulance and stroke clinicians conducting triage consultations will be conducted by researchers who will be based in the stroke unit. We will conduct observations only with written consent from stroke clinicians and verbal consent from both ambulance clinicians and patients; the researcher will only enter the space where the consultation is taking place once consent has been provided by all and commence taking written fieldnotes; no patient-identifiable information will be recorded/noted in these fieldnotes (*further details provided under 'consent', overleaf*).

With all observations, if at any point the clinicians feel it has become inappropriate for the observation to continue, they will inform the researcher of this, and the researcher will withdraw.

8 CONSENT

Stakeholder interviews

Researchers will approach potential participants initially by sharing study information (Participant Information Sheet) by e-mail or post. The Participant Information Sheets explain the purpose and nature of the research, what participation involves, its benefits (or lack of benefits), risks, and burdens. The Participant Information Sheets also make clear that there is no obligation to participate, and that participants are free to refuse to participate or withdraw up to 14 days after the interview with no implication for their care or status. To enable a wide range of participation, the recruitment documents will be professionally translated into 12 commonly spoken non-English languages.

Potential participants will be given at least 48 hours to decide whether they would like to take part in the interview. If participants would like to take part remotely they will be asked to complete a consent form (written or electronic) and return it to the research team in advance of the interview. If individuals would like to take part in an interview, a mutually convenient time and platform (phone, teams or zoom) will be decided.

A member of the research team will consent participants. Individuals will be asked to complete consent forms (written or electronically) prior to taking part in the interview. Participants who complete the consent form by hand will be asked to sign two copies (one for the researcher and one for the participant). Participants who consent electronically will be sent a copy of the completed consent form for their records. Participants will be asked to return the consent form

in one of two ways: a) posting the consent form back to the researcher, or b) emailing the consent form back to the researcher (either by scanning a handwritten copy or by completing the consent form electronically). Participants will be asked to send the consent form in advance of the interview. Interviews will not take place unless the researcher has received the signed consent form. Participants will have the opportunity to ask questions at any time. Interpreter services will be provided to support participants who do not have English as a first language.

Non-participant observations of professional activity

Prehospital video triage assessments: We have developed our approach to obtaining consent for observations in collaboration with our clinician and patient collaborators. Observations of ambulance and stroke clinicians conducting triage consultations will be conducted by researchers who will be based in the stroke unit.

Researchers will obtain written consent from all stroke physicians providing prehospital video triage in advance of observations commencing. It will not be possible to seek individual consent from all ambulance clinicians involved in prehospital video triage, therefore before commencing any observations, researchers will attend ambulance staff meetings to discuss the research and obtain verbal consent from ambulance teams. Similarly, it will not be possible to obtain written consent from suspected stroke patients; therefore, the clinicians conducting the assessment will obtain patient verbal consent for these observations of professional activity to be conducted before the researcher enters the space where the triage assessment is to be conducted.

When the stroke clinician is alerted to an incoming triage call, the researcher will withdraw so that the researcher can neither see nor hear the initial discussion between clinicians and patient. If the stroke clinician and ambulance clinician conducting the triage assessment are satisfied that the patient has capacity to give consent, they will ask the patient for verbal consent for the observation to take place. If the clinicians are not satisfied that the patient has capacity to give consent, and no observation will take place. If the patient provides verbal consent, and the clinicians are still satisfied that the patient has capacity to provide this consent, the clinicians will invite the researcher to enter the space where the triage consultation is being conducted, so that the researcher may commence taking fieldnotes. No patient-identifiable information will be recorded/noted in these fieldnotes

With all observations, if at any point the clinicians feel it has become inappropriate for the observation to continue, they will inform the researcher of this and the researcher will withdraw immediately.

Meetings and training activities: Permission to observe the meetings will be obtained from the Chair/session lead in advance of the meeting taking place. Agreement for the observation to take place will also be requested from those taking part in the meeting and agreement will be documented in the minutes.

All participant data will be treated anonymously, and will not be identified by name in any reports. As with the interviews, these activities will be conducted only with full ethical and research governance approvals.

Workstream 2. Patient conveyance, care delivery, and patient outcomes

The hypothesis is that prehospital video triage will a) reduce the number of inappropriate patient transfers to specialist stroke units, which will b) result in hyperacute treatments being delivered to stroke patients more quickly and reliably than elsewhere, and therefore c) that stroke patients treated by such services will have better outcomes than those treated by services that do not use prehospital video triage. To test these hypotheses, the analysis will use a controlled before-and-after design to estimate the impact of prehospital triage on ambulance journeys for suspected stroke patients:

Patient destination: the hypothesis is that there will be a significant reduction in the proportion of patients classified as 'suspected stroke/neurological' who are transferred to hospitals with specialist stroke units following implementation of prehospital triage services, relative to control sites.

The study will also analyse 'Job cycle' length (i.e., time from initial 999 call received through to 'ambulance free'), disaggregated by key processes (Table 4)

Furthermore, the analysis will estimate the impact on stroke patients receiving key clinical interventions, including:

- Time from onset of symptoms to receiving clinical interventions (to assess potential impact of increased time on scene to conduct prehospital triage)
- Time from arrival at hospital to receiving clinical interventions (to assess potential benefits of prehospital triage and advance knowledge of patients on effective running of stroke teams)
- Impact of these services on the following key outcomes
 - Patient mortality at 90 days (the primary outcome)
 - Patient functional outcome (as measured with the Modified Rankin Scale)

These patient-level analyses will compare areas using prehospital triage (NC London, East Kent, Maidstone and Darent Valley) with other areas of England where prehospital triage is not used (hereafter referred to as the 'comparator') (Table 3), using propensity score matching (taking care to use only patient variables that should not be altered by the triage intervention, e.g. sex and age).^[32] A difference in differences (DiD) approach will be employed to understand the impact of the 'treatment effect' prehospital triage on outcomes (primary outcome: patient mortality at 90 days). DiD aims to generate causal effect estimates by comparing the change in the outcome from before to after the introduction of an intervention in the group exposed to the intervention, to the change in outcome from before to after the intervention in a group not exposed to the intervention. Provided a valid control group has been identified, the difference between the two differences can be said to represent the impact of the intervention.

As outlined above, the analysis will include a minimum of 12 months 'before' data and up to 26 months 'after' data. Given the sample sizes (Table 4), the team do not anticipate concerns about statistical power, but during the early stages of the study researchers will engage with clinical partners and data owners to understand the data in depth, and will conduct robustness tests alongside the main analyses.

Workstream timeline:

- Months 1-5: researchers work with clinical collaborators and data owners to gain a deeper understanding of the data available, specify data requests.
- Months 5-15: data requests submitted and data received to be prepared for analysis.
- Months 13-22: main analyses conducted, leaving time for integration of findings (see WS4).

Workstream 3: cost-effectiveness [RQ4; months 1-24]

In addition to understanding the effectiveness of pre-hospital triage it is also important to evaluate the cost-effectiveness of the intervention. Where possible the analyses will seek to understand if different triage systems deliver variable outcomes and costs, thereby informing any wider national scale-up.

The health economic analysis will focus on the case study sites and national and regional controls (Table 3). The analyses will draw on the same data sources as requested for Workstream 2 (Table 4), along with national reference costs and Trust estimates of service costs.

The analyses will estimate the costs of prehospital triage (from NHS and personal social services perspectives). Estimated outcomes (life years or quality-adjusted life years) will be derived from the outcomes in the data and evidence in the literature. The analyses will estimate cost-effectiveness as the difference in cost between comparators divided by the difference in outcomes to give an incremental cost-effectiveness ratio (ICER) per life year saved and per quality-adjusted life year gained. A DiD analysis will be used to determine the effect size, while the cost of care will be estimated using national reference costs further informed by exploring the resource use and cost of prehospital triage systems, captured in interviews with Trusts.

The economic evaluation will compare the costs and outcomes of pre-hospital triage to no triage using decision analytic modelling.^[33] Patient pathways will follow those of published papers including Hunter et al 2018,^[16, 18] amended for the triage setting. The researchers will work with clinicians to determine the appropriateness of published models and any need to amend the pathway and stroke management given pre-hospital triage. Analysis of patient subgroups will be guided in part by the data and also confirmed with clinicians as to whether the subgroups are clinically relevant and feasible in terms of informing broader adoption decisions.

The time horizon will be ten years, this aligns with other similar literature.^[16, 18, 33, 34] Mortality estimates will be derived from the linked HES/ONS data. Quality-adjusted life year (QALY) estimates will be derived from the literature that has evaluated stroke interventions including those addressing delays in presentation. The analyses will also apply QALY estimates to other events that can be documented in the linked data, such as length of stay and readmissions where these are available in the literature.^[16, 18, 33, 34] The base case analysis will consider the incremental cost per QALY gained, additionally the analysis will also estimate the additional cost per life year gained, as a sensitivity analysis, on the expectation that there will be minimal primary QoL data specific to pre-hospital triage. Other sensitivity and scenario analysis will be undertaken in order to evidence the uncertainty in the economic evaluation results, including the estimation of cost effectiveness acceptably curves and net monetary benefit estimates.^[16, 18, 33] The analysis will undertake budget impact modelling to understand future implementation costs and cost savings and to which part of the health care system they accrue.

Workstream timeline:

- Months 1-4: data specification.
- Months 7-15: data requests and preparation, interviews with Trust to understand resource implications of prehospital triage, including any additional training and implementation costs
- Months 16-24: data analysis and integrating findings (see WS4).

Missing data

While the ambulance, SSNAP, and HES/ONS datasets have high levels of participation/completeness, we acknowledge that there may be some missing data. Further, this issue may have become more pronounced during the COVID19 pandemic. The team also recognise that it is possible that missing data may occur systemically rather than randomly in these datasets.^[35] In response, sensitivity analyses will be conducted, employing a reference-based multiple imputation approach, as recommended in current best practice guidelines with respect to addressing missing data and why it is missing.^[35, 36]

Workstream 4: integrating analyses, generating lessons, stakeholder workshop (RQ5; months 2-24]

The analyses will be integrated throughout the study in monthly team meetings. There will also be three key stages of integration, where researchers on Workstreams 1, 2, and 3 will work with clinical and patient collaborators.

- Months 1-4: ensuring study designs are complementary (e.g. qualitative research explores issues that may emerge from the quantitative) for presentation to and feedback from Study Steering Committee (SSC).
- Months 10-12: generating interim lessons to share with stakeholders and SSC; researchers will incorporate feedback into research design (e.g. additional quantitative/economic measures or interview topics).
- Months 20-24: identifying key lessons to be shared with SSC and incorporating feedback from final SSC meeting. A stakeholder workshop will identify how lessons may apply to different settings. The workshop will be conducted both digitally and in-person (to maximise accessibility) and themes fed into the final report.

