- First, the study will analyse how prehospital triage was set up, run, and experienced by patients, carers, and staff. Interviewees will include patients and carers; stroke, ambulance, and emergency teams; and service and system managers. Non-participant observations will be conducted on oversight and delivery of prehospital triage, and documents related to how the services are working will be analysed. The analysis will focus on how the services were put into action, and what helped or hindered this. We will also ask patients and carers how they experienced prehospital triage.
- Second, the study will analyse the impact of prehospital triage on healthcare services and patient outcomes. NHS data will be studied to analyse whether introducing prehospital triage results in: more patients being taken to the right hospital service; more patients remaining at home and avoiding hospital admission; patients (stroke and nonstroke) getting the right care more quickly, and if there are any adverse effects of prehospital triage; and improving how well patients do after their stroke. Analyses will compare performance before and after prehospital triage was introduced. Analyses will also compare the areas that are using prehospital triage with other parts of the UK that are not currently using it.

• Third, the study will analyse whether prehospital video triage services are delivering good value for money to the NHS. Again, analyses will compare performance before and after prehospital triage was introduced. Analyses will also compare the areas that are using prehospital triage with other parts of the UK that are not currently using it.

Throughout, the team will engage with people leading prehospital triage in monthly meetings, so they can make use of the findings as they develop. The team will develop a list of clinicians, politicians, charities, members of the public, and others who make decisions about healthcare and are interested in the research; the team will share quarterly newsletters and podcasts to describe how the research is going. The team will share the findings at research conferences and in academic journals, and make accessible summaries and videos for stakeholders. Finally, the team will run a workshop for people providing stroke and other services, patients and carers, charities, and international experts, to share and develop lessons for services across the UK that might want to introduce prehospital triage.

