2 BACKGROUND AND RATIONALE

Stroke is a major cause of death and disability.^[1] Stroke patients have better care and outcomes if treated in a specialist unit.^[2-5] Not every hospital has a specialist stroke unit: patients are commonly triaged by prehospital clinicians, bypassing the nearest emergency department if a patient is thought to be suffering a stroke. Many patients present with stroke-like symptoms but have another condition which 'mimics' a stroke. This may be difficult to determine in the prehospital setting with the assessment deemed 'false positive',^[6] and the patient making an unnecessary journey to a specialist stroke team when in fact an alternative health care setting may be more appropriate (comprising up to 50% of all presentations to specialist stroke teams). This places avoidable pressure on ambulance and stroke services, with serious implications for quality of care for stroke and non-stroke patients.^[7] Remote prehospital triage may increase appropriate patient transfer, improving effectiveness and efficiency of ambulance, stroke, and other services, and the quality of care and outcomes for stroke and non-stroke patients.

During the first wave of the COVID19 pandemic, ambulance, and stroke teams in North Central (NC) London and East Kent developed and implemented prehospital video triage services, which used digital tools technology to permit remote communication between ambulance clinicians and stroke specialists. Through these services, stroke specialists can assess the patient while the patient is still on scene of the 999 call. The aim was to optimise individual patients' care: to ensure that stroke patients were taken to a stroke unit, and to minimise the number of non-stroke patients making unnecessary journeys to a stroke unit or hospital emergency departments (ED) if they could be managed by their GP or as an outpatient; these issues are important at any time, but became particularly urgent during the pandemic.

Reviewing existing evidence

Through a current service evaluation (discussed below),^[8] the team are conducting a two-phase literature review to assess the existing evidence base. The initial phase was a 'review of reviews' to identify existing systematic, scoping and narrative reviews on prehospital triage for

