	Patients categorised by ambulance crews as suspected stroke/neurologica	 Job cycle length, disaggregated by Time to dispatch; to scene; on scene; to hospital; Total job cycle Patient destination 	Aug 2022
Local stroke units	Patient-level	Stroke services using prehospital triage are collecting data on destination and diagnosis of all patients categorised as non-stroke	Apr 2019- Aug 2022
SSNAP	Patient-level Data for patients categorised as stroke	 Type of stroke (infarction/haemorrhage) Stroke severity (NIHSS¹) on arrival Patient characteristics (e.g. sex, age) Arrival mode (e.g. by ambulance, inhospital) Eligibility for thrombolysis Eligibility for mechanical thrombectomy Time from a) symptom onset, b) 999 call, and c) arrival at hospital to brain scan admission to stroke unit thrombolysis (if eligible) mechanical thrombectomy (if eligible) assessment by consultant physician assessment assessment by stroke specialist nurse swallow screen Outcomes: Functional independence: patients with Modified Rankin Scale score (established measure of stroke patient disability) of 0-2 (or return to baseline if baseline score is more than 2)	Apr 2019- Aug 2022
HES/ONS	Patient-level ED attendances (with dates); Stroke attendances	Emergency hospital admissions with dates and length of hospital stay All-cause patient mortality at 30 and 90 days	Apr 2019- Aug 2022

Note. ¹NIHSS=National Institutes of Health Stroke Scale.

Workstream 3: cost-effectiveness [RQ4; months 1-24]

In addition to understanding the effectiveness of pre-hospital triage it is also important to evaluate the cost-effectiveness of the intervention. Where possible the analyses will seek to understand if different triage systems deliver variable outcomes and costs, thereby informing any wider national scale-up.

The health economic analysis will focus on the case study sites and national and regional controls (Table 3). The analyses will draw on the same data sources as requested for Workstream 2 (Table 4), along with national reference costs and Trust estimates of service costs.

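### The destination test counts every fall in conveyance to stroke-unit hospitals as support for hypothesis (a), and no named outcome measures strokes that triage missed or diverted

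*Protocol*

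**What the plan says.** Protocol section 9, Workstream 2, opens with a three-step hypothesis. Step (a) is that triage will "reduce the number of inappropriate patient transfers to specialist stroke units". The destination outcome that tests it is stated as an expectation that "there will be a significant reduction in the proportion of patients classified as 'suspected stroke/neurological' who are transferred to hospitals with specialist stroke units", relative to control sites. The denominator is every patient so coded by the crew, and final diagnosis plays no part.

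Two other statements set a wider standard. Section 2 gives the purpose of the services as "to ensure that stroke patients were taken to a stroke unit, and to minimise the number of non-stroke patients making unnecessary journeys", which has two sides. Section 1 promises to examine "if there are any adverse effects of prehospital triage".

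The other Workstream 2 outcomes in section 9 are job-cycle length, times to clinical intervention, 90-day mortality (primary) and "Patient functional outcome (as measured with the Modified Rankin Scale"). Time from onset to intervention is included "to assess potential impact of increased time on scene to conduct prehospital triage".

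Table 4 in section 4 lists one source with a diagnosis for patients whom triage judged not to have a stroke: services using triage are "collecting data on destination and diagnosis of all patients categorised as non-stroke". The text after Table 3 says that data collected by the triage stroke teams will be analysed, but not for what measure.

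**The concern.** The hypothesis concerns inappropriate transfers, while the test counts all transfers. A triage error that keeps a stroke patient away from the stroke unit is the failure that the section 2 aim is meant to prevent, yet it adds to the fall that is read as success. If followed exactly, the plan could declare (a) confirmed partly because strokes were misdirected.

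The remaining outcomes do not clearly close this gap. Section 9 frames step (c) on stroke patients treated by the services, and Table 4 limits the SSNAP data to patients categorised as stroke. A stroke that was left at home and never recognised may enter neither. One that went first to another hospital may enter, but nothing marks it as diverted.

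Section 20 expects the findings to inform national policy and local pathways, so a destination result that cannot separate good triage from poor triage matters.

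**Working it through.** The protocol gives no effect size, event rate or power figure to reproduce. The check therefore has three parts: a comparison of the texts, the size of the denominator, and an illustration.

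**1. Texts side by side**
- Hypothesis (a): inappropriate transfers.
- Test of (a): all suspected stroke/neurological patients, in one direction.
- Section 2 aim: strokes to a stroke unit and non-strokes elsewhere.
- Section 1: a check for adverse effects, with no measure named there.
- Section 9: no outcome for a stroke that triage sent elsewhere or left at home.
- Local stroke-unit records: no under-triage measure in section 9; no control, because only triage services collect them; a window from April 2019, although Table 1 starts the services between April and November 2020; and the units are absent from the quantitative data sources in section 12.

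**2. How much of the denominator is stroke (Table 3, annual)**
- Strokes: 970 + 1,457 + 789 + 515 = 3,731.
- Calls: 1,729 + 2,529 + 2,620 + 984 = 7,862.
- Ratio: 3,731 / 7,862 = 0.475 (East Kent 56%, NC London 58%, Maidstone 30%, Darent Valley 52%).

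This is a rough upper figure, because not every stroke arrives by ambulance. The protocol says that the vast majority do.

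**3. Illustration (assumptions not taken from the protocol)**

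Assume that 80% are conveyed to a stroke-unit hospital at baseline, with 12 months before, 24 months after, and no clustering. The standard error of a four-cell difference-in-differences is sqrt(sum of p(1−p)/n).

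Take a 10-point fall: 0.10 × 7,862 = 786 calls a year.
- SE = sqrt(0.16/7,862 + 0.21/15,724 + 0.16/46,724 + 0.16/93,448) = 0.0062.
- z = 0.10 / 0.0062, about 16, so power exceeds 99%.

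The estimate and its power are the same for any stroke share among those diverted:

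| Stroke share of diverted | Strokes diverted a year | Share of 3,731 |
|---|---|---|
| 0% | 0 | 0% |
| 5% | 39 | 1.1% |
| 10% | 79 | 2.1% |
| 20% | 157 | 4.2% |

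Now ask whether 90-day mortality would reveal this. Assume 15% baseline mortality and 5 to 20 points of excess mortality per missed stroke. Suppose also that every missed stroke enters the analysis, which favours detection.
- SE = sqrt(0.1275 × (1/3,731 + 1/7,462 + 1/85,549 + 1/171,098)) = 0.0073.
- Shift detectable at 80% power, two-sided 5%: (1.96 + 0.84) × 0.0073, about 2.0 points.
- Shift from 79 missed strokes: 79 × 0.05 / 3,731 = 0.1 point, to 79 × 0.20 / 3,731 = 0.4 point. Power is about 4% to 8%.
- With 157 missed strokes the shift is 0.2 to 0.8 point and power about 5% to 21%.

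Clustering would lower all of these powers.

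**The case against.** A reader might infer that the promised check for adverse effects has no outcome at all. The documents do not support that. Mortality, the Modified Rankin Scale and onset-to-intervention time can each move in the harmful direction. Mortality comes from HES linked to ONS, so a diverted stroke later admitted and coded elsewhere can still be counted. A diverted stroke that reaches a stroke unit late lengthens the onset and 999-call times. These outcomes are insensitive to missed strokes, not absent.

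Nor are the triage teams' records wholly unused, since section 4 says that they will be analysed. Their lack of a control is inherent, because control areas make no triage decision.

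It would also be too broad to say that the problem is the same at every site. Table 1 shows the emergency department and stroke unit co-located at Maidstone and Darent Valley, which supply 2,620 + 984 = 3,604 of 7,862 calls (46%). A stroke redirected to the on-site emergency department there does not lower the proportion.

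A reader could also reach alarming totals by supposing that triage diverts at random: 373 strokes a year at 10% diversion (0.10 × 3,731) and 1,119 at 30% (0.30 × 3,731). Nothing in the protocol supports random diversion by stroke clinicians, and these totals place every stroke among the calls.

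Destination is not the primary outcome, and Workstream 1 and the preceding rapid evaluation address safety in other ways. Neither is described as a controlled measure of under-triage.

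Finally, a statistical analysis plan not at hand may define a harm measure. The mismatch between hypothesis and test nevertheless stands in the protocol's own text, and a later plan cannot use a data field that was never requested.

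**Conclusion.** The concern holds in a limited form. The test of (a) cannot distinguish appropriate from inappropriate diversion, and no named outcome measures strokes that were missed or diverted. At the two sites with co-located departments, this applies only to patients left at home or sent to another hospital.

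That the measure ignores diagnosis follows from the text and needs no assumption. The 0 to 157 strokes a year rest on an assumed 10-point fall and an assumed stroke share of 0% to 20%. The mortality powers rest on the assumed baseline and excess mortality. None of this shows that strokes are being misdirected, only that the destination result would not reveal it and that mortality would be unlikely to. The window and section 12 points are accurate but administrative. This should be fixed, but it does not invalidate the primary analysis.

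**What to change.** 1. Keep the destination proportion as a process measure, and state that (a) will not be concluded from it alone.
2. Name an under-triage outcome in HES, analysed by the same difference-in-differences: the proportion of stroke admissions preceded within 7 and 30 days by an emergency department attendance or admission at another hospital. Separate out direct inter-hospital transfers within the same episode, since Table 1 describes three of the sites as centralising. Report the estimate and confidence interval beside the destination result, and do not read a non-significant rise as evidence of safety. State that this measure misses strokes left at home and later taken straight to a stroke unit.
3. To cover those, ask the ambulance services for a repeat-contact identifier, which Table 4 does not list. Where it is available, report repeat calls after a first call that was not conveyed or was diverted. Note that the extract holds only calls coded suspected stroke/neurological.
4. Use the local stroke-unit records for an uncontrolled estimate, by site and after each start date, of the share of patients triaged as non-stroke who were finally diagnosed with stroke. Correct that row's window in Table 4 and add the units to section 12.

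The cost is protocol wording, some extra analysis and possibly one more data field. The destination result could no longer be reported as a benefit on its own.
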